The purpose of this novel patient-facing disease management intervention, **My Diabetes GOAL**, is to develop and test a system embedded within the electronic medical record to engage patients in personalized goal setting and chronic disease management by: 1) establishing personalized goals of care based on comorbidities and preferences, 2) tracking diabetes measures against personalized goals, and 3) selecting the route and intensity of care management to help patients achieve their goals (e.g., telephonic care management, in-person care management, and self-care resources). This application can be used to individualize care, increase engagement with patient portals, and improve patient self-efficacy, as they take a more active role in their care.

3. Description of Protocol Methodology:

We will conduct a 6-month randomized controlled trial comparing My Diabetes GOAL vs. usual care within University of Chicago clinics (endocrinology, primary care group, and geriatrics). After agreeing to participate, patients will be randomly assigned to each arm, for a total of 50 patients per arm. Patients that are enrolled in the intervention arm will receive an email message via MyChart to complete the initial questionnaire. If there is an initial non-response, we will try three additional times over a one month period. Completion of the questionnaire will be required prior to initiating risk factor tracking and opening the portal to requests for care management support. Patients enrolled in the usual care will receive the My Diabetes GOAL survey with a 6 months delayed start.

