Prior to receiving the survey, they will be able to continue to receive routine diabetes care and education provided by diabetes educators and clinical staff. Upon completion the study, all patients will receive a post-survey via MyChart. Electronic Health records will be a critical source of data on key processes of care that are affected by My Diabetes GOAL including goal setting measures (documenting personalized goals of diabetes care, proportion following ADA recommendations, proportion choosing alternative goals) as well as referrals to care management and frequency of phone contacts. The EHR will also be the primary source of data for risk factor levels (glycosylated hemoglobin, blood pressure, cholesterol levels), medications, and health care utilization (outpatient visits, care management services, ER visits, and hospitalizations). These data are continually collected as a part of routine care.

4. Duration:

The initial MyChart survey should not take more than 10 minutes to complete. The post-survey should not take more than 5 minutes to complete. Enrollment in services or receipt of telephonic care management is up to the patient, and dependent on their responses to the survey questions. After 6 months, we will terminate telephonic care management follow-up phone calls.

5. Exact Location:

The surveys will be conducted online.

6. Special precautions: n/a

7. Experimental controls:

50 control patients will receive a delayed intervention so we can compare usual care versus the intervention arm, but still distribute the survey and potential telephonic care management to the control arm at a later date. Patients will be the units of randomization. We will enroll patients over 65 years of age with active MyChart accounts, diagnosis of type 2 diabetes, and outpatient clinic visit in the prior year. Because of the general purpose of the intervention, we will not exclude patients with comorbid illnesses or functional impairments. We plan to enroll 100 patients. We will determine trial arm assignment through a random number generator.

8. Outcome measures:

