The primary endpoint is documentation of a personalized goal for diabetes care (e.g., A1C target) (yes or no) in 6 months. Secondary endpoints include patient engagement with MyChart, patient selection of personalized goals, patients' ability to reach their personal treatment goals. We will also collect data on hypoglycemia, psychosocial measures, and health care utilization. It is also possible that changes in patient reported outcomes and utilization will occur earlier than expected through mechanisms that are separate from changes in drug prescribing and risk factor control.

The **documentation measures** (utilization of MyChart, documenting personalized goals of diabetes care, proportion following ADA recommendations, proportion choosing a goal different from the ADA recommendations) will be assessed by comparing results from the EHR at baseline (6 month lookback) and at 6 months of the trial. For **short-term clinical outcomes**, we will evaluate changes

in the proportion of patients with out-of-range A1Cs (A1C>9.0%, A1C<6.5% taking insulin/sulfonylureas) and blood pressures (BP>150/90, BP<120/65). We will also assess changes in the proportion of patients taking statins and specific glucose lowering agents. These analyses will be done for the overall population along with comparisons of drug use by the ADA risk strata. To evaluate **health care utilization**, we will again utilize the EHR to determine the frequency of referrals to telephone care management, the source of referrals (population management, physician), the patient predictors of referrals, and to characterize frequency and content of telephonic management.

9. Statistical analysis:

For the primary endpoint analysis, we will use the Fisher's exact test, and the logistic regression model to compare the two groups. We will also use both the generalized linear mixed model (GLMM) and the generalized estimating equation (GEE) to model % documentation over time (at baseline and 6 months) and test the effects of treatment, time, and interaction between treatment and time. We will first fit unadjusted model and then adjust for potential risk factors such as age, gender, race, and its baseline outcome. Within-subject correlation will be taken into account.

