For the analyses of secondary endpoints, we will conduct between-cohort analyses for those outcomes which can be obtained for both groups, mainly through EHR, and conduct within-cohort analyses for those outcomes which can be collected only in the intervention group.

For between-cohort analyses, for the repeated-measured continuous outcomes such as A1c and BP, we will use a linear mixed model (LMM) to model the outcome over time and test the effects of treatment, time, and treatment-by-time interaction. For the repeated-measured binary outcome such as utilization of MyChart and following ADA recommendations, the same statistical methods as for the primary endpoint will be applied. A Wilcoxon's rank-sum test, and the bootstrapping method will be used to compare frequencies of each type of health care utilization (primary care, emergency room, and hospital visits) for prior 6 months, at baseline and 6 months, and their changed frequencies at 6 months from baseline, respectively. A GEE will also be used to model the frequencies of health care utilization over time.

For within-cohort analyses, i.e., within the intervention group, for the continuous outcome (which will be measured once during the study) such as patient engagement with MyChart, a multiple linear regression will be performed to test the time trend, i.e., conduct self-comparison (post versus before). For the repeated measured binary outcome such as patients' awareness of their A1c goal, both GLMM and GEE will be used to test the time trend. For the binary outcome (which will be measured once during the study) such as achieving their A1c goal at 6 months, the logistic regression model will be used to test the time trend.

We will repeat the analysis plan above, if necessary, at 12 months for the available outcomes from EHR for sustainability check between the groups and/or within cohort.

Power and sample size justification: The primary outcome is documenting personalized goals of diabetes care in 6 months. We expect that at baseline, in both groups, there would have <5% patients whose charts have been documented their personalized goals. We presume that the intervention group will have more than 50%. Using the Fisher's exact test, a total sample size of 44 subjects (22 per group) is needed to obtain at least 90% power to detect the difference between the two groups at a two-sided significance of 5%. With a total sample size of 100, the power will be >0.99.

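### Awareness of the A1c goal is analysed only as a before-after trend in the intervention arm; a randomised 6-month comparison is available at small cost if controls answer before their delayed survey

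*Combined protocol and SAP*

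**What the plan says.** Section 9 sorts the secondary outcomes by where they can be measured. On one side, "we will conduct between-cohort analyses for those outcomes which can be obtained for both groups, mainly through EHR"; on the other, the plan will "conduct within-cohort analyses for those outcomes which can be collected only in the intervention group". Awareness is given as an example of the second kind: for patients' "awareness of their A1c goal, both GLMM and GEE will be used to test the time trend". No between-arm analysis of awareness appears anywhere.

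Section 3 says: "Upon completion the study, all patients will receive a post-survey via MyChart". It also says: "Patients enrolled in the usual care will receive the My Diabetes GOAL survey with a 6 months delayed start". Until then, "they will be able to continue to receive routine diabetes care and education provided by diabetes educators and clinical staff". Section 7 gives the reason for the delay: "50 control patients will receive a delayed intervention so we can compare usual care versus the intervention arm".

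For the primary endpoint, section 9 says that "we will use the Fisher's exact test, and the logistic regression model to compare the two groups".

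**The concern.** A before-after trend in one arm answers whether awareness changed among intervention patients. It does not answer whether it changed more than under usual care. Secular change and routine diabetes education could both raise awareness. Controls keep receiving that education, and nothing in the documents says it stops in the intervention arm, so the trend cannot separate these influences from the intervention.

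The trial has a randomised usual-care arm and a survey that reaches it. If controls are sent their delayed My Diabetes GOAL survey before anyone asks them about awareness, an unexposed 6-month control value can no longer be obtained. The stake is the interpretability of one minor patient-reported outcome. The primary endpoint and the EHR comparisons are not affected.

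**Working it through.** **1. The passages side by side.**
- Within-cohort analysis is reserved for outcomes that only the intervention group can supply (section 9).
- The post-survey goes to everyone (section 3), so a channel for a patient-reported item exists in both arms.
- The between-cohort rule relies on the EHR mainly, not solely, so it does not shut out survey outcomes.
- Section 9 calls awareness a repeated measure, which implies a measurement before the intervention takes effect and a later one. A form of the item that does not need a goal set by the intervention therefore looks feasible.
- Not stated: the items on either survey, and whether controls answer the post-survey before or after their delayed survey. Section 13 also describes a MyChart survey invitation after consent without distinguishing arms.

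**2. The plan's own figure.** The documents give no figure for awareness. For the primary endpoint they state 22 per group for at least 90% power (Fisher, 5% vs 50%, two-sided 5%) and power above 0.99 with 100 patients. Exact power is the sum over x and y of Bin(x; n, p1) × Bin(y; n, p2), taken over the tables where Fisher's p ≤ 0.05. It gives 0.894, 0.911 and 0.927 at n = 20, 21 and 22 per group, and 0.9998 at 50. Both stated figures are supported, and the same routine is used in step 4.

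**3. The one-arm test when the intervention has no effect.** All rates here are assumptions. Take p0 = 40% aware at baseline and p1 = 50% or 55% at 6 months from background change alone. The joint probability of being aware at both visits is p11 = p0·p1 + ρ√[p0(1−p0)p1(1−p1)] for ρ = 0.2 or 0.5, or p11 = 0.9·p0 if 90% of those aware stay aware. For the 10-point rise with ρ = 0.5, p11 = 0.20 + 0.5 × 0.245 = 0.3225, so 7.75% lose awareness and 17.75% gain it. With 90% retention, p11 = 0.36, so 4% lose it and 14% gain it.

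The GEE time test is z = (logit p̂1 − logit p̂0)/SE, with SE² = [v0 + v1 − 2(p̂11 − p̂0p̂1)v0v1]/n and vt = 1/[p̂t(1−p̂t)]. It was simulated with 400,000 trials per cell. McNemar is exact. Percentage of trials significant, in the order ρ = 0.2 / ρ = 0.5 / 90% retention:

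| Responders | Rise | GEE | McNemar |
|---|---|---|---|
| 50 | 10 points | 21 / 30 / 38 | 14 / 20 / 26 |
| 50 | 15 points | 40 / 58 / 64 | 30 / 45 / 52 |
| 30 | 10 points | 16 / 23 / 29 | 8 / 10 / 10 |
| 30 | 15 points | 28 / 43 / 49 | 16 / 23 / 25 |

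With baselines of 20%, 40% and 60% and 50 responders, the GEE range is 21% to 49% for 10 points and 40% to 75% for 15. With no rise, GEE rejects in 4.3% to 5.4% at n = 50.

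**4. The randomised comparison at 6 months.** If the arms share the same 6-month rate (30% to 75%), Fisher rejects in 3.0% to 3.5% with 50 per arm and 2.5% to 2.7% with 30. Its power, again under assumed rates:

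| Responders per arm | 40% vs 70% | 40% vs 60% |
|---|---|---|
| 50 | 83% | 46% |
| 40 | 72% | 37% |
| 30 | 56% | 26% |

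**5. Differential response.** Suppose 50% are aware in both arms, aware and unaware intervention patients respond at 90% and 70%, and all controls respond at 70%. Intervention responders then show (0.5 × 0.9)/(0.5 × 0.9 + 0.5 × 0.7) = 0.45/0.80 = 56%, against 50% in controls: a spurious 6 points.

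**The case against.** The plan specifies a valid test, labels it within-cohort and does not call it a treatment effect. A reader might infer that section 9 misclassifies awareness and so contradicts section 3. The documents do not support that. They list no survey items and do not fix when controls answer. If controls answer only after their delayed survey, no unexposed value exists and the classification is right.

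There is also a plausible reason for the one-arm choice. The outcome concerns the patient's own goal, and section 9 expects fewer than 5% to have a documented one at baseline, so many controls may have no personalised goal to be aware of. This stands as a condition on the fix: the item must be worded so that such a patient can answer it.

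Finally, the benefit is modest. Power is low for a 20-point difference, the comparison rests on responders, controls have no baseline value, and every awareness rate used here is assumed. All of this stands. It limits what the comparison can deliver, but the one-arm trend offers no comparison with usual care at all.

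**Conclusion.** A minor, inexpensive improvement, conditional on timing. As planned, the awareness analysis can describe change in the intervention arm but cannot serve as evidence of an effect against usual care. A randomised comparison is within reach if controls can answer at 6 months while still unexposed.

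The rejection rates in step 3 might be read as an inflated type I error. They are not: awareness did change in those scenarios, so the test correctly rejects no change over time. They mislead only if the result is taken as an intervention effect. Their size depends on the assumed baseline, rise, within-patient correlation and number of responders. The conclusion that a one-arm trend lacks a usual-care comparison depends on none of these.

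**What to change.** - State the post-survey items and when each arm receives the survey.
- Put the same awareness item on the post-survey for all randomised patients, including intervention patients who never completed the initial questionnaire. Word it so that a patient without a documented personalised goal can answer, for example whether the patient knows an A1c target, with no target counted as not aware.
- Send it to controls at 6 months, before their My Diabetes GOAL survey is released. Make clear that the invitation in section 13 does not bring that survey forward for controls.
- Use the same reminders in both arms and report response by arm.
- Move awareness to the between-cohort analyses and compare arms at 6 months by Fisher's exact test or logistic regression. Keep the intervention-arm change as descriptive.
- If controls cannot answer before the delayed survey, leave the analysis within-cohort and say that it does not estimate an effect against usual care.

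The cost is one survey item and its definition, the order of two MyChart messages, post-survey reminders (the documents describe reminders only for the intervention arm's initial questionnaire) and a few sentences of SAP text. One limitation remains: intervention patients are asked twice and controls once, so the comparison cannot separate the initial questionnaire from the rest of the intervention.

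### A1c-goal attainment is recorded once, at 6 months and in one arm, so the logistic regression planned in section 9 has no time trend to test

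*Combined protocol and SAP*

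**What the plan says.** Section 8 (Outcome measures) lists "patients' ability to reach their personal treatment goals" among the secondary endpoints. Section 9 (Statistical analysis) splits the secondary analyses in two: between-arm analyses for outcomes available in both groups, and a second set in which the investigators will "conduct within-cohort analyses for those outcomes which can be collected only in the intervention group". A1c-goal attainment is in the second set. The sentence that covers it begins "For the binary outcome (which will be measured once during the study) such as achieving their A1c goal at 6 months" and ends "the logistic regression model will be used to test the time trend".

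The same paragraph of section 9 provides two points of comparison:

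- For a continuous outcome, MyChart engagement, it explains a time trend as comparing patients with themselves, after against before.
- For a repeatedly measured binary outcome it plans correlated-data methods: patients' "awareness of their A1c goal, both GLMM and GEE will be used to test the time trend".

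A1C itself comes from the EHR. Section 3 says of the EHR data: "These data are continually collected as a part of routine care". The 6-month lookback in section 8 is stated for the documentation measures, which are assessed "by comparing results from the EHR at baseline (6 month lookback) and at 6 months of the trial". No baseline status for goal attainment is defined anywhere.

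**The concern.** A trend over time needs at least two time points. The sentence supplies one, and because the analysis is confined to the intervention arm there is no control contrast to take its place.

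A1c-goal attainment is the only goal-attainment analysis that section 9 names, and reaching personal goals is a listed secondary endpoint. If the text stays as it is, the analyst will have to devise a different analysis at the end of the trial, possibly with the data in view. The obvious candidates (a proportion, a test against 50%, a before-after test on a derived baseline) answer different questions.

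**Working it through.** **The plan's own figure.** Section 9 gives no rate, precision or power for this outcome. Its only calculation is for the primary endpoint, and it reproduces: the exact power of Fisher's test at 5% versus 50% is 0.927 with 22 per group and above 0.999 with 50 per group. It plays no part in this point.

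**Step 1: can the stated model be fitted?** Inputs from section 9: intervention arm only, one binary record per patient, at 6 months. For patient *i* the model is

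logit P(Yᵢ = 1) = β₀ + β₁·tᵢ, with tᵢ = 6 for every *i*.

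The linear predictor is β₀ + 6β₁ for everyone, so only that sum is estimable. The rank of the design matrix shows the same:

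| Data | Columns | Rank |
|---|---|---|
| One record each, n = 25, 50 or 1000 | 2 | 1 |
| One record each, n = 50, plus two covariates | 4 | 3 |
| Baseline and 6-month records, n = 50 | 2 | 2 |

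Covariates and larger samples do not help; a second time point does. What remains is the intercept, and its p-value tests whether attainment equals 50%, which is not a trend.

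**Step 2: what the missing baseline hides.** Take 25 of 50 at goal at 6 months and assume 3 patients lose the goal. With B at goal at baseline, the number gaining it is 25 − B + 3. The exact McNemar p-value is 2·P(X ≤ 3), where X ~ Binomial(gained + 3, ½), capped at 1.

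| At goal at baseline | Gained / lost | p |
|---|---|---|
| 10 | 18 / 3 | 2 × 1562 / 2²¹ = 0.0015 |
| 15 | 13 / 3 | 2 × 697 / 2¹⁶ = 0.021 |
| 20 | 8 / 3 | 2 × 232 / 2¹¹ = 0.23 |
| 25 | 3 / 3 | 1.0 |

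The 6-month data are identical in all four rows.

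**Step 3: what each repair could deliver.** The documents give no attainment rate, so these figures rest on assumptions. I take n from 25 (half the arm, since section 9 presumes more than 50% will have a documented goal) to 50.

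*Single 6-month proportion*, exact (Clopper-Pearson) 95% interval: 13/25 gives 31% to 72%; 25/50 gives 36% to 64%.

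*Paired before-after test*, assuming 25% gain the goal and 5% lose it (a net rise of 20 points) from a baseline of 30% or 40%, two-sided 5%, summed over all possible outcomes:

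| Method | Power, n = 50 | Power, n = 25 |
|---|---|---|
| GEE, robust Wald | 80% | 53% to 54% |
| Exact McNemar | 70% | 30% |
| Logistic regression ignoring pairing | 55% | 21% to 24% |

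With no true change (baseline 40%, 10% gain, 10% lose), rejection rates in the same order are 4.8%, 2.2% and 0.3% at n = 50, and 6.1%, 0.9% and 0.3% at n = 25. Ignoring the pairing therefore costs power here and does not inflate false positives. GEE is slightly liberal at n = 25.

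Exact McNemar reaches 80% power at a net rise of about 23 points (n = 50) or 39 points (n = 25) if 5% lose the goal, and about 29 or 46 points if 10% do.

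**The case against.** The best defence is that measurement once during the study leaves room for a value from before it. A1C is collected routinely, and the paragraph itself explains a time trend as an after-versus-before comparison. On that reading there are two records and a time effect is estimable. Conditional logistic regression is also a logistic model and, with one binary time term, tests the same hypothesis as McNemar.

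The reading is possible, but it does not rescue the text. No baseline attainment status is defined, conditional logistic regression is not named, and the authors assign GLMM and GEE to repeated binary outcomes while giving this one the single-measure method. For the primary endpoint's repeated model they add that "Within-subject correlation will be taken into account"; nothing similar is said here.

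The possible 12-month repeat does not help either. It is conditional, and it is described as running the analyses again to check sustainability, not as a second time point in this model.

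Three further objections have force:

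- The power figures rest on assumed rates, and the number with both an A1C goal and a 6-month A1C could fall below 25, because section 8 gives an A1C target only as an example of a personalized goal.
- Section 9 expects fewer than 5% to have a documented goal at baseline. A baseline status would therefore be constructed by applying a later goal backwards, and it may depend on how that goal was chosen.
- The stakes are limited: this is one uncontrolled secondary analysis, and no stated decision depends on it.

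These bear on the choice of repair and on severity. They do not remove the defect.

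**Conclusion.** The concern holds, with high confidence. As written, the time-trend test for A1c-goal attainment cannot be run at any sample size. This follows from the sentence itself and needs no assumed rates. If a baseline status was intended, the plan must define it and name a paired method, so the sentence needs correcting on either reading.

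Severity is should-fix, at the minor-to-moderate end. The primary endpoint and sample size stand, and A1c as a continuous outcome has its own between-arm mixed model.

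A side point, as an ambiguity only: MyChart engagement is also described as measured once and yet compared with before, and the plan does not say whether an earlier value exists.

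**What to change.** For A1c-goal attainment, choose one and write it into section 9.

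**(a) Keep the single measure.** Delete the time-trend test. Report the 6-month proportion at goal, with an exact 95% confidence interval, among patients who set an A1c goal. Give the proportion over all randomised intervention patients as a supporting figure. This is sufficient on its own; the cost is losing the before-after test.

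**(b) Define a baseline status.** Apply each patient's chosen goal to the baseline EHR A1C where one exists. State the window for that A1C: eligibility requires a clinic visit in the prior year, not an A1C. Test the change with McNemar, or with the GEE or GLMM already planned for repeated binary outcomes. Describe it as an uncontrolled before-after comparison against a goal applied retrospectively. It is limited to goal-setters with an A1C at both times.

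Under either option, say how a goal-setter without a 6-month A1C is handled, since A1C comes from routine care.

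For MyChart engagement, state whether a before value exists. If it does, analyse the per-patient change or use a repeated-measures model. If not, drop the comparison and describe the 6-month value. If engagement is the same measure as MyChart utilization, the between-arm analysis already in section 9 applies.

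The cost is wording and a little analysis time, with no change to the primary endpoint, sample size or patient contact.
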